3.1 Study Design

Prospective, randomized, multi-center, clinical study. Up to twenty centers will randomize up to 350 subjects who are candidates for a Total Shoulder Arthroplasty, to 2 treatment groups in a 2:1 (Eclipse: Univers II) fashion. FDA has agreed that randomization of controls may be halted after N=77, with continuing enrollment of Eclipse until the originally planned Eclipse sample size target is reached. Given the timing needed for approval to stop control enrollment, the actually number of evaluable randomized controls may be slightly larger. This study will cease enrollment and be terminated if the Eclipse Shoulder Prosthesis receives 510 (k) clearance prior to all subjects completing the study.

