10.4 Sample Size Analysis for Primary Non-Inferiority Test

Given the above criteria, the Sponsor expects a success rate of 88% for both the Eclipse and control group.

To determine the required sample size, it was assumed that the above primary hypotheses will be tested using 1-sided $\alpha=0.05$ at a statistical power of at least 80%. Under these assumptions, nQuery Advisor 7.0 module PTE0U-1 produces the following:

“When the sample sizes in the groups are 98 and 196, a two-group large-sample normal approximation test of proportions with a one-sided 0.05 significance level will have 80% power to reject the null hypothesis that the test and the standard are not equivalent (the difference in proportions, $p_T - p_S$, is -0.10 or farther from zero in the same direction) in favor of the alternative hypothesis that the proportions in the two groups are equivalent, assuming that the expected difference in proportions is 0.00 and the proportion in the standard group is 0.88.

Therefore, the total number of Per Protocol (Efficacy Evaluable) patients required under these assumptions are $N=294$. The number of protocol violations of inclusion / exclusion criteria (i.e., randomized in error) is expected to be small. The randomized sample size is adjusted up by 15% to account for both loss-to-follow-up and exclusions due to protocol violation to $N=347$.

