10.7 Safety Analysis

All safety endpoints will be summarized separately for investigational and control groups. Similarly, listings with details of the specific complications will be summarized separately as well.

The CCS Component Safety endpoint is any serious, definitely device-related adverse event within 24 Months of surgery. This will be evaluated at the exact two year anniversary (i.e., relative day 730) after the implantation surgery. The safety hypothesis of investigational verses control equality in the likelihood of serious device-related adverse event will be tested using a two-sided Fisher's Exact Test with Type I error rate set to $\alpha=0.05$.

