10.8 Treatment of Missing Data

As previously described, patient success will be defined at Month 24 postoperatively on the basis of a Composite Clinical Success (CCS) criterion. If the Month 24 CCS endpoint is missing due to a clinical evaluation (i.e., Constant score or radiographic results) unavailable at the Month 24 interval but available at a later date (i.e., after the end of the Month 24 interval), the later clinical evaluations will be used to impute missing values. The roll-back imputation is typically considered conservative since in most orthopedic study, maximum recovery is achieved earlier than 24 Months.

It is expected that there will be at least a few patients with missing Month 24 CCS despite the use of Month 24+ roll-back for clinical and radiographic components of the Month 24 CCS. A tipping point analysis will be performed in order to assess the impact of missing data on primary non-inferiority comparisons. Sequentially, at each stage of the tipping point analysis, one missing Month 24 CCS in the investigational device group will be considered as a failure while at the same time one missing value in the control group will be considered a success. Tipping point stages will be sequentially assessed until there are no more missing CCS values in either group.

If the percentage of missing CCS is more than small, e.g., >10%, then the primary sensitivity analysis will involve multiple imputation (Rubin DB, 1991) (MI) rather than tipping point analysis.

MI minimizes the effects of selection bias on the estimates of the proportions achieving Month 24 CCS. A logistic regression method for monotone missing data using SAS procedure Proc.MI (SAS Institute INC, 2006) will be employed to produce multiply imputed outcome determinations for patients missing Month 24 CCS. This method first fits a

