logistic regression model for the outcome variable based on covariates using complete cases. Then, based on the fitted regression model, a new logistic regression model is simulated from the posterior predictive distribution of the parameters which is then used to impute the missing outcome variables. This is done by using the model to compute the expected probability of clinical success for each patient missing the outcome. A uniform random number from 0 to the patient specific expected probability is then generated and if the value is less than the expected probability, the outcome is imputed as a success, otherwise impute the outcome as failure. After all missing outcomes are imputed, the estimated proportion and its standard error will be determined in the usual way. This process will be repeated 20 times. The final point estimate will be determined as the mean value over these 20 multiple imputations. The final standard error used to construct the 95% confidence interval needed for the primary non-inferiority test will be determined from the pooled variance (within imputation variance) plus a term reflecting variability among the 20 multiply imputed point estimates (between imputation variance) (Rubin DB, 1986). The final estimate and 95% confidence interval will be computed by the SAS procedure Proc.MIANALYZE using this approach. By imputing the missing values among patients with missing Month 24 CCS, bias is reduced since the inference is to the entire population that includes patients both missing and not missing Month 24 CCS. The standard error of the final estimate accounts for the statistical uncertainty present in the imputed outcomes and so confidence intervals tend to have the correct coverage rates.

11 Bibliography

Blackwelder, W. (1982). Proving the null hypothesis. *Controlled Clinical Trials*, 3:345-353.

Bohsali KI, W. M. (2006). Complications of total shoulder arthroplasty. *J Bone Joint Surg* , 88, 2279-2292

Boileau, P., et al., *Cemented polyethylene versus uncemented metal-backed glenoid components in total shoulder arthroplasty: a prospective, double-blind, randomized study*. *J Shoulder Elbow Surg*, 2002. **11**(4): p. 351-9.

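### Section 10.4 gives 80% power only for 98/196, although section 3.1 lets control enrolment stop at 77 (about 74%), and section 10.8's 95% interval for the non-inferiority test has no stated sidedness

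*Combined protocol and SAP*

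**What the plan says.** **Level.** Section 10.4 sets the level for the primary test: "it was assumed that the above primary hypotheses will be tested using 1-sided" alpha of 0.05, with power of at least 80%. It then reports the software result for 98 control and 196 Eclipse evaluable patients: "a two-group large-sample normal approximation test of proportions with a one-sided 0.05 significance level will have 80% power to reject the null hypothesis". Section 10.2 (Primary Efficacy Hypothesis) gives the hypotheses and the 0.10 margin but no level and no interval.

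The only interval that the plan connects to this test is in section 10.8, in the text on multiple imputation: "The final standard error used to construct the 95% confidence interval needed for the primary non-inferiority test". The same section adds: "The final estimate and 95% confidence interval will be computed by the SAS procedure". Neither sentence states sidedness. Imputation has a limited role: if more than about 10% of composite outcomes are missing, "then the primary sensitivity analysis will involve multiple imputation". Section 10.7, by contrast, is explicit for its own comparison: the serious device-related "adverse event will be tested using a two-sided" Fisher's exact test.

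**Sample size.** Section 10.4 requires 294 evaluable patients (98 + 196) and then adds an allowance: "The randomized sample size is adjusted up by 15% to account for both loss-to-follow-up and exclusions due to protocol violation", giving 347. Section 3.1 says: "FDA has agreed that randomization of controls may be halted after N=77, with continuing enrollment of Eclipse" up to the Eclipse target first planned. It adds that the count of evaluable controls may end slightly above 77, without giving a number. Section 10.4 has no calculation for this reduced control arm.

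**The concern.** There are two separate problems, and the second is the weightier.

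1. **Ambiguous decision level.** A one-sided 0.05 test corresponds to the lower limit of a two-sided 90% interval, which is the same as a one-sided 95% bound. An unqualified 95% confidence interval is usually read as two-sided, and its lower limit tests at one-sided 0.025. On that reading the imputation analysis would use a different threshold from the primary analysis. A sensitivity analysis should change only the assumption about missing data. If it also changes the level, a disagreement with the primary result cannot be put down to missing data. The two-sided reading is the stricter one, so false non-inferiority claims are not at issue.

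2. **Power not stated for the permitted design.** A reader of 10.4 takes away at least 80% power. That holds for 98 controls, which section 3.1 no longer requires. With 21 fewer controls (98 − 77) the chance of missing true non-inferiority is higher than the plan tells its readers.

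**Working it through.** **Inputs.** True success rate p = 0.88 in both arms, evaluable sizes 98 and 196, one-sided 0.05 and the 15% allowance, all from 10.4; margin 0.10 from 10.2 (Primary Efficacy Hypothesis); control stop at 77 from 3.1. Assumption: 77 and 196 are evaluable counts. The reference in 3.1 to evaluable controls supports this for 77.

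**Formula** (large-sample normal approximation, the method named in 10.4):

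SE = √[p(1 − p)(1/n_C + 1/n_E)]; power = Φ(0.10/SE − z), with z = 1.645 (one-sided 0.05) or 1.960 (one-sided 0.025).

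**The plan's own figures.** SE = √[0.88 × 0.12 × (1/98 + 1/196)] = 0.0402. Then 0.10/0.0402 = 2.487 and Φ(2.487 − 1.645) = 80.0%. With 97 controls the result is 79.8%, so 98 is the smallest control arm that works. Inflation: 98/0.85 and 196/0.85, each rounded up, give 116 + 231 = 347. Both figures reproduce.

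**Control stop.** With 77/196, SE = √[0.1056 × (1/77 + 1/196)] = 0.0437, 0.10/SE = 2.288, and power = Φ(2.288 − 1.645) = 74.0%. The table adds other control numbers, the stricter level, and exact binomial enumeration of the unpooled Wald test at 88%/88%.

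| Controls / Eclipse | SE | Formula, 0.05 | Exact, 0.05 | Formula, 0.025 | Exact, 0.025 |
|---|---|---|---|---|---|
| 98 / 196 | 0.0402 | 80.0% | 81.9% | 70.1% | 72.1% |
| 90 / 196 | 0.0414 | 78.0% | 80.3% | 67.6% | 70.2% |
| 80 / 196 | 0.0431 | 75.0% | 77.7% | 64.0% | 66.3% |
| 77 / 196 | 0.0437 | 74.0% | 77.3% | 62.9% | 64.6% |

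By exact enumeration 80% is first reached at 89 controls (80.2%; 88 controls give 79.9%).

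Other readings and methods, all at one-sided 0.05:
- 77 randomized controls with 15% lost leave 77 × 0.85 ≈ 65 to 66 evaluable: 69.3% to 69.8% with 196 Eclipse.
- 231 evaluable Eclipse patients (the inflated Eclipse figure, none lost) with 77 controls: 75.6%.
- Farrington–Manning variance, which is not the plan's named test: 83.0% at 98/196 and 79.5% at 77/196.

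Every variant at 77 controls is below 80%.

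**What the level does.** The largest observed Eclipse shortfall that still passes is 0.10 − z × SE. At 98/196 this is 3.39 points at one-sided 0.05 and 2.12 points at 0.025. At 77/196 it is 2.81 and 1.43 points.

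A worked case with complete data uses 86/98 control successes (87.8%) and the unpooled Wald SE. The limit to beat is −10 points.

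| Eclipse successes of 196 | Lower limit, two-sided 90% | Lower limit, two-sided 95% | Outcome |
|---|---|---|---|
| 165 | −10.50 | −11.83 | fails both |
| 166 | −9.96 | −11.28 | passes 90% only |
| 167 | −9.41 | −10.73 | passes 90% only |
| 168 | −8.86 | −10.17 | passes 90% only |
| 169 | −8.32 | −9.62 | passes both |

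These results isolate the effect of the level. They are not the power of the imputation analysis, nor a rate at which it would disagree with the primary analysis.

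**The case against.** **On the level.** Section 10.4 states the primary level plainly, and the plan writes two-sided where it means it (10.7), so an unqualified 95% could be read as the complement of 10.4's 0.05. On that reading nothing conflicts. The interval also belongs to a sensitivity analysis that may never be run: later visits are first used to fill missing Month 24 evaluations, and only then does the threshold of about 10% apply. The 15% in 10.4 covers exclusions as well as loss to follow-up, so it is not the same quantity as missing composite outcomes.

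Much of this stands. The point is an ambiguity and not a proven contradiction, and the primary decision under 10.4 is unaffected. It does not remove the need for a clarification. The sentence in 10.8 itself links the interval to the primary test, the conventional reading is two-sided, and 10.4 expects eligibility violations to be few. Most of the 15% is therefore an allowance for loss to follow-up, and more than 10% missing remains plausible even after later visits are used.

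**On power.** The statement in 10.4 is conditional on 98 and 196 and is true as a calculation. The stop is optional, openly disclosed and agreed with FDA, and the control count may exceed 77. By exact enumeration the loss is under 5 points (81.9% to 77.3%).

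It is right that the arithmetic in 10.4 is sound and that the loss depends on the test. But agreement to stop does not supply a power figure, the excess over 77 is not quantified, and no method tried reaches 80% at 77/196.

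**Conclusion.** The concern holds on both parts and should be fixed.

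- **Power (main part).** The 80% in 10.4 does not describe the design that 3.1 permits. Power at 77/196 is 74.0% by the plan's method and 77.3% by exact enumeration. This rests on 88% success in both arms and on 77 and 196 being evaluable counts. It rises to 75.0% with 80 controls and 78.0% with 90, and falls to about 69% to 70% if 77 is a randomized count with 15% lost.
- **Level (lesser part).** Section 10.8 leaves open whether its 95% interval is a one-sided bound, which matches 10.4, or a two-sided interval, which is one-sided 0.025. At 98/196 the choice moves power from 80.0% to 70.1% and the passing shortfall from 3.4 to 2.1 points. The harm is a possible uninterpretable mismatch between analyses, not a raised false-positive risk.

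**What to change.** 1. In 10.2 (Primary Efficacy Hypothesis) and 10.8, state that non-inferiority is concluded when the lower limit of the two-sided 90% confidence interval (equivalently a one-sided 95% bound) for the Eclipse minus Univers II difference is above −0.10. Apply this rule to the primary, tipping-point and multiple-imputation analyses alike.
2. Only if a two-sided 95% interval is really intended, say so and restate power as about 70% at 98/196 and about 63% at 77/196.
3. In 10.4, keep the 98/196 calculation and add the power under the control stop in 3.1: about 74% at 77/196 by the plan's method and 77% by exact enumeration. State whether 77 and the Eclipse target are evaluable or randomized counts, and show the range for other control numbers.

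**Cost.** A wording amendment to section 10, which needs FDA and IRB approval under 8.16, and a less favourable stated power. Items 1 and 3 need no additional patients and leave the test level in 10.4 unchanged.

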10.5 Analysis of Baseline Differences and Poolability

10.5.1 Description of demographics and baseline characteristics

Demographic and baseline characteristics will be tabulated and compared between the investigational group and control group. Variables to be compared will include baseline shoulder assessment, disease severity, age, gender, limb dominance, primary diagnosis, Body Mass Index (BMI), weight, and height. Descriptive p-values will be determined using Wilcoxon rank sum tests for continuous measures and chi-square or exact tests for categorical variables. However, focus will be on clinical significance of group differences and only secondarily on p-values, since these p-values are not associated with planned comparison. If there are clinically significant group differences for any baseline variable, then multiple logistic regression will be used to assess the impact of controlling for the baseline variable on conclusion. Specifically, the odds ratio for achieving Month 24 CCS

comparing investigational group to control group will be computed with and without including the baseline variable in question. If the odds ratio changes by less than 15%, it will be concluded that the primary results are not confounding by device group imbalance for that variable (Mickey RM, 1989).

10.5.2 Description of site differences at baseline

Demographic data, primary diagnosis, and summary clinical measures will be tabulated by investigative site. Interval measures will be compared among sites using analysis of variance (ANOVA) (Scheffe, 1959). Frequency distributions will be compared among sites using chi-square statistics or generalized exact tests (Mehta CR, 1983), as appropriate. For statistical comparisons only, sites contributing less than 10 eligible procedures will be combined.

10.6 Survival Analysis

For each relevant cohort, life-tables will be tabulated indicating the number of device failures and the number of at-risk procedures over time. Since the number of patients at risk (i.e., those being followed) diminishes over time, Peto's method (Peto T, 1977) will be used to determine standard errors for estimates of cumulative survival. Kaplan-Meier survival curves (Kaplan EL, 1958) will be plotted for investigational and control devices on the same graph to facilitate graphical comparisons of survivorship over time. The secondary hypothesis of equal survival distributions between groups will be tested using a log-rank statistic (Mantel N, 1959). Comparisons among sites in device survival will be performed using log-rank statistics (Mantel, 1966) and Cox regression (Cox, 1972). In some analyses, sites contributing fewer than 10 patients will be combined.

10.7 Safety Analysis

All safety endpoints will be summarized separately for investigational and control groups. Similarly, listings with details of the specific complications will be summarized separately as well.

The CCS Component Safety endpoint is any serious, definitely device-related adverse event within 24 Months of surgery. This will be evaluated at the exact two year anniversary (i.e., relative day 730) after the implantation surgery. The safety hypothesis of investigational verses control equality in the likelihood of serious device-related adverse event will be tested using a two-sided Fisher's Exact Test with Type I error rate set to $\alpha=0.05$.

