Appendix 2-10 Constant Shoulder Score Physician Investigator Examiner Section115

Appendix 2-11 Summary of MMT Functions:118

Appendix 2-11 Constant Score Calculations120

1 Protocol Summary

Title:	A Prospective, Randomized, Multicenter Study Comparing the Safety and Effectiveness of ArthroX's Eclipse™ Shoulder Prosthesis to the Univers™ II Shoulder Prosthesis in Patients with a Degenerative Joint Disease
Purpose:	The purpose of this study is to demonstrate non-inferiority of the ArthroX Eclipse™ Shoulder Prosthesis to the ArthroX Univers™ II Shoulder Prosthesis for the treatment of degenerative joint disease in subjects who are candidates for total shoulder replacement. Non-inferiority in terms of safety and effectiveness will be measured by a 2 year composite clinical success (CCS) that requires functional improvement, radiographic success, absence of reoperations and revision, and lack of serious device-related adverse events.
Study Design:	Prospective, randomized, multi-center, clinical study, up to 20 sites will randomize up to 350 subjects who are candidates for a Total Shoulder Arthroplasty, to 2 treatment groups in a 2:1 (Eclipse: Univers II) fashion. This study will cease enrollment and be terminated if the Eclipse Shoulder Prosthesis receives 510 (k) clearance prior to all subjects completing the study.
Study Hypothesis:	The goal of the study is to determine that the Eclipse™ Shoulder Prosthesis is non-inferior to the Univers™ II Shoulder Prosthesis.
Investigational Arm:	ArthroX Eclipse™ Shoulder Prosthesis (Eclipse)
Control Arm:	ArthroX Univers™ II Shoulder Prosthesis (Universe II)

- Study Population:** The population for this study will consist of males and females 21 years of age and older who are candidates for a total shoulder joint replacement where the humeral head and neck are of sufficient bone stock and the rotator cuff is intact or re-constructible for one of the following indications: Osteoarthritis, avascular necrosis, post-traumatic arthritis, or rheumatoid arthritis. Additionally, the subject is not a candidate for a hemi-humeral arthroplasty and has continued symptoms in target shoulder despite at least six months of other treatment modalities (anti-inflammatory, physical therapy and steroid injections).

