10.2 Primary Efficacy Hypothesis

The primary efficacy hypothesis for this study is formulated in terms of clinical non-inferiority and is consistent with the Blackwelder approach (Blackwelder, 1982). Symbolically, the null and alternative hypotheses may be expressed as follows:

Ho: $\pi_{\text{Eclipse}^{\text{TM}}} - \pi_{\text{Univers II}^{\text{TM}}} \leq -\delta$ (investigational device inferior)

Ha: $\pi_{\text{Eclipse}^{\text{TM}}} - \pi_{\text{Univers II}^{\text{TM}}} > -\delta$ (investigational device not inferior)

The π represents the proportion (or probability) of devices expected to achieve Month 24 Composite Clinical Success. Thus, this study is designed to demonstrate that π for investigational device is no more than δ less than π among control devices. For $\delta = 0.10$, these hypotheses may be written as:

Ho: $\pi_{\text{Eclipse}^{\text{TM}}} - \pi_{\text{Univers II}^{\text{TM}}} \leq -0.10$

Ha: $\pi_{\text{Eclipse}^{\text{TM}}} - \pi_{\text{Univers II}^{\text{TM}}} > -0.10$

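### The only formal stand-alone safety comparison is a two-sided test of equality with no interval for the difference; at plausible low event rates it could not show comparable safety

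*Combined protocol and SAP*

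**What the plan says.** Section 10.7 (Safety Analysis) defines the endpoint: "The CCS Component Safety endpoint is any serious, definitely device-related adverse event within 24 Months of surgery", assessed at day 730. It then says that the "safety hypothesis of investigational verses control equality in the likelihood of serious device-related adverse event will be tested" by a "two-sided Fisher's Exact Test with Type I error rate set to $\alpha=0.05". The section gives no margin, expected rate, power, confidence interval for the difference or rule for reading the result. Sections 10.7.1 and 10.7.2 add event counts and listings by group.

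The formal safety claim sits elsewhere. The Purpose entry of the Protocol Summary (Section 1) says: "Non-inferiority in terms of safety and effectiveness will be measured by a 2 year composite clinical success (CCS"). Section 3.2.2 makes freedom from serious device-related complications one of the requirements for CCS. The Primary Efficacy Hypothesis (Section 10.2) tests CCS against a margin of 0.10, and Section 10.4 sizes the trial for that test alone.

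Section 4.1.2 summarises safety endpoints in the Per Protocol cohort. Section 3.1 allows randomization of controls to halt after 77, with Eclipse enrolment continuing to its original target.

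**The concern.** An equality null is suited to finding a difference. Failing to reject it says little unless the test had a good chance of rejecting when harm was real. Here the event is narrowly defined and probably uncommon, the sample size comes from a different endpoint, and the control arm may be smaller than planned. A p-value alone cannot distinguish data that rule out a material excess from data that are simply sparse.

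At stake is what the trial can say about serious device-related harm taken by itself. If the Eclipse rate were two or three times the control rate at low absolute levels, the planned test would usually miss it, and the report would contain no interval showing how large an excess remains compatible with the data.

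**Working it through.** **Inputs from the documents.** Evaluable sizes: "When the sample sizes in the groups are 98 and 196" (control and Eclipse; Section 10.4). CCS test: "tested using 1-sided $\alpha=0.05$ at a statistical power of at least 80"%. Expected CCS: "the Sponsor expects a success rate of 88% for both the Eclipse and control group". Margin 0.10 (Section 10.2). Allowance for loss and exclusion 15% (Section 10.4). Possible control number 77 (Section 3.1), taken here as evaluable; that section says it may end slightly larger.

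**Assumed input.** The documents state no rate for the safety event, so I use control rates of 1% to 5%. The upper end has a loose anchor: expected CCS failures are 12%, the score threshold alone is expected to fail about 7% (Section 10.1), and 12 − 7 = 5 points remain for all other components if failures do not overlap.

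**1. The plan's own figure.** Control n = (1.645 + 0.842)² × [0.88×0.12 + 0.88×0.12/2] / 0.10² = 6.183 × 0.1584 / 0.01 = 97.9, so 98 control and 196 Eclipse, 294 in all. Then 98/0.85 → 116 and 196/0.85 → 231, total 347. Both figures reproduce. None of this concerns the safety test.

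**2. Power of the planned safety test.** Power = Σ Bin(x; 196, p_E) × Bin(y; n_C, p_C), summed exactly over all (x, y) with two-sided Fisher p ≤ 0.05.

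| Control v Eclipse rate | 196 v 98 | 196 v 77 |
|---|---|---|
| 1% v 2% | 1% | 0.3% |
| 2% v 4% | 7% | 4% |
| 3% v 6% | 14% | 11% |
| 5% v 10% | 27% | 21% |
| 1% v 3% | 5% | 2% |
| 2% v 6% | 26% | 20% |
| 5% v 15% | 74% | 64% |

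Against a 2% control rate, 80% power needs an Eclipse rate of about 10.6% (11.8% with 77 controls). With no control events, significance needs at least 9 Eclipse events (11 with 77 controls). By normal approximation, 80% power for 2% v 4% would take about 891 control and 1,782 Eclipse patients.

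**3. What an interval would add.** The Newcombe interval for d = p_E − p_C, with Wilson limits (l, u) for each arm, is d − √[(p_E − l_E)² + (u_C − p_C)²] to d + √[(u_E − p_E)² + (p_C − l_C)²].

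- Illustration A, rate doubled: 8/196 (4.08%) v 2/98 (2.04%). Wilson limits are 2.08% to 7.85% and 0.56% to 7.14%. Lower limit: 2.04 − √(2.00² + 5.10²) = −3.4 points. Upper limit: 2.04 + √(3.77² + 1.48²) = +6.1 points. Fisher p = 0.50.
- Illustration B: 11/196 (5.6%) v 1/77 (1.3%) gives p = 0.19 and an interval of −1.9 to +8.6 points. With 98 controls the same counts give p = 0.067, so this example sits at the unfavourable end.
- Illustration C: 4/196 v 2/98, identical rates, gives p = 1.00 and an interval of −5.2 to +3.4 points.

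A and C are both plainly non-significant, yet the upper limits differ: +6.1 against +3.4 points. The p-value does not convey this.

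**4. Can the CCS test stand in?** Suppose the event rate rises from 2% to 6% and each extra event is an extra CCS failure, so CCS is 84% v 88%. SE = √(0.84×0.16/196 + 0.88×0.12/98) = 0.0420. The chance of still declaring non-inferiority is Φ[(−0.04 + 0.10)/0.0420 − 1.645] = Φ(−0.216) = 41%. With 77 controls, SE = 0.0454 and the chance is 37%. The composite reacts (80% falls to 41%), but it passes a tripled event rate in roughly two trials of five. Any offsetting gain on another component would raise that.

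**5. Endpoint definition.** Section 10.7 requires a definite device relationship, but the relatedness scale in Section 9.2 ends at probably related. The CCS definition in Section 10.1 describes the component as a severe, not a serious, device-related event. These sections need reconciling. A narrower definition would lower the counts and reduce power further.

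**The case against.** The strongest reply is that the safety claim does not depend on the Fisher test. The Protocol Summary and Section 3.2 place it on CCS, which counts serious device-related complications and reoperations as failures and is tested with a proper non-inferiority null. On that view the Fisher test is an extra look at one component, and an unpowered comparison of that kind is common. This is correct as to where the formal claim rests. It answers the concern only in part, because of step 4.

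A reader might infer that the sponsor will treat a non-significant Fisher result as proof of comparable safety. The documents do not say so. Section 10.7 gives a hypothesis, a test and an alpha, with no rule for reading the result. The defensible statement is that non-significance would not support such a conclusion, and that the plan is silent on the matter.

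A reader might also infer that the test has almost no power in general. That goes too far. The rates are assumptions, and at 5% v 15% power is 74% or 64%, so a large safety signal would probably be found.

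Finally, Sections 10.6 to 10.7.2 provide life-tables, survival curves and a log-rank test for device failure, together with event counts and listings. A reader could compute the risk difference from the group summaries. That is true, but none of these is a planned interval for the difference on this endpoint.

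**Conclusion.** The point holds as a limit on what the planned test can show. For control rates of 1% to 5%, which are assumed, power to detect a doubling stays below 30% at either control size. At 2% to 3% it is about 7% to 14% with 98 controls and 4% to 11% with 77. For 2% v 6% it is 26% or 20%. The test is useful only for large differences. A non-significant result would not show comparable safety, and the CCS test with its 10-point margin does not fill the gap for a moderate rise in this one component.

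The primary analysis and its sample size are unaffected. The power figures take 196 Eclipse patients and 98 or 77 controls as evaluable. Using all randomized patients (231 v 116) changes little: 2% v 4% then has about 10% power and 2% v 6% about 33%.

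**What to change.** In Section 10.7:

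- Make the Eclipse-minus-control risk difference, with a two-sided 95% Newcombe (or exact) confidence interval, the main result for serious device-related adverse events to day 730.
- Keep the two-sided Fisher p-value, labelled descriptive.
- State that a non-significant p-value is not evidence of equal safety.
- Treat the interval as estimation only. If a separate safety claim is intended, prespecify and justify a margin for the upper limit; without a stated limit, judging safety on the upper bound is not a decision rule.

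This takes a few sentences and one extra table column. It needs no new data or patients and leaves the primary test unchanged. The downside is that the reported safety result may look less favourable, because the interval will show how large an excess the data cannot exclude.
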